#### **9.2 Statistical methods**

The Type I error probability associated with this test of this null hypothesis is 0.05. We will use an uncorrected chi-squared statistic to evaluate this null hypothesis.

### **10.0 Confidentiality, Privacy and Data Management**

See attached Research Data Plan Review form

### **11.0 Data and Safety Monitoring Plan**

This is a low risk therapeutic study with an agent with a known safety profile.

#### **11.1 Periodic evaluation of data**

The PI and research coordinator will review cumulative adverse events, early termination of study participation, and accrual every six months and report any issues requiring modification of the study or alteration of the risk:benefit ratio to the IRB immediately. A summary of adverse events, study progress

and protocol modifications will be included for IRB review in the continuing review.

## **11.2 Data that are reviewed**

The data to be reviewed will be:

- Safety data
- Untoward events
- Efficacy data

## **11.3 Method of collection of safety information**

Safety information will be collected by the research staff preoperatively and post operatively as described in Section 7.2.

## **11.4 Frequency of data collection**

Data and adverse events assessments begin after the patch is placed on the subject. The research staff will evaluate the subject preoperatively on the day of surgery and then follow postoperatively with a personal or phone interview 120 hours postoperatively when the patch is removed. A second and final phone interview will be performed 7 days after patch removal.

## **11.5 Individual's reviewing the data**

Oversight for the conduct of the study will be provided by the PI and the research coordinator will monitor the data. They will ensure that all eligible criteria and consent requirements are met prior to a subjects' participation in the study and that the procedures and adverse event reporting occur according to the IRB approved protocol.

## **11.6 Frequency of review of cumulative data**

The PI and research coordinator will review cumulative adverse events, early termination of study participation, and accrual every six months and report any issues requiring modification of the study or alteration of the risk:benefit ratio to the IRB immediately. A summary of adverse events, study progress and protocol modifications will be included for IRB review in the continuing review.

## **11.7 Statistical tests**

Not applicable

## **11.8 Suspension of research**

The decision to suspend research will be based on the assessment of all serious adverse events for causality and the decision to stop the trial definitively would be based on the related events that are unexpected and change in frequency of events.

## **12.0 Risks**

### **12.1 CONTRAINDICATIONS**

Sancuso is contraindicated in patients with known hypersensitivity to granisetron or to any of the components of the patch.

### **12.2 WARNINGS AND PRECAUTIONS**

#### **12.2.1 Gastrointestinal**

The use of granisetron in patients may mask a progressive ileus and/or gastric distention caused by the underlying condition.

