### 3.2 Exclusion Criteria

- Allergy to granisetron or other 5HT3RA drugs
- Previous allergic reactions to any drug skin patches
- Recent (less than 1 month) or current chemo- or radiotherapy
- Any nausea, vomiting, or retching within 24 hours prior to anesthesia
- Any type of eye surgeries
- History or diagnosis of gastrointestinal obstruction or ileus
- History of serotonin syndrome
- Unable to sign consent

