#### **7.2.1 Visit 1 - Anesthesia Preoperative Evaluation Clinic and recruitment and drug dispensation**

Patient is seen in clinic and identified as having a history of serious PONV, in particular delayed or post discharge PONV. Study will be explained to the patient and consent obtained. The investigational pharmacy will be notified that a study patient has been enrolled and they will prepare the patches for distribution to the patient. EKG will be performed and the results will be recorded preoperatively.

A member of the research team will obtain the assigned patches from the investigational pharmacy and deliver to the anesthesia provider (member of the research team).

The provider will then demonstrate to the patient how to apply the patch and the patient can practice using a placebo patch to show that the correct placement. Patient will then take the actual patch home with them. Patient will also be given a PONV diary to take home with them. Upon returning home from surgery, the patient will be asked to record their instances of nausea and vomiting on a daily basis for up to five days after surgery. At hour 120 post-op, a case manager will telephone the patient and note any recorded

instances of nausea and vomiting since the patient has returned home. The case manager will also check the status of the patch and any medications that were taken as a result of nausea and vomiting. One week after removal of patch (120h post-op + 7 days), a case manager will call the patient a final time to collect adverse events and to assess patient satisfaction with the patch.

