#### **7.2.4 Visit 3- Follow-up for possible side-effects**

The patient will be contacted by phone to record any possible side-effects they may have experienced since the removal of the patch.

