## **12.3 ADVERSE REACTIONS**

### **12.3.1 Clinical Trials Experience**

Because clinical trials are conducted under widely varying conditions, adverse reaction rates observed in the clinical trials of a drug cannot be directly compared to rates in the clinical trials of another drug and may not reflect the rates observed in clinical practice.

The safety of Sancuso was evaluated in a total of 404 patients undergoing chemotherapy who participated in two double-blind, comparator studies with patch treatment durations

of up to 7 days. The control groups included a total of 406 patients who received a daily dose of 2 mg oral granisetron, for 1 to 5 days.

Adverse reactions occurred in 8.7% (35/404) of patients receiving Sancuso and 7.1% (29/406) of patients receiving oral granisetron. The most common adverse reaction was constipation that occurred in 5.4% of patients in the Sancuso group and 3.0% of patients in the oral granisetron group.

Table 1 lists the adverse reactions that occurred in at least 3% of patients treated with Sancuso or oral granisetron.

**Table 1: Incidence of Adverse Reactions in Double-Blind, Active Comparator Controlled Studies in Cancer Patients Receiving Chemotherapy (Events  $\geq$  3% in either group)**

Body System Preferred Term	Sancuso TDS N=404 (%)	Oral granisetron N=406 (%)
Gastrointestinal disorders		
Constipation	5.4	3.0
Nervous system disorders		
Headache	0.7	3.0

5-HT3 receptor antagonists, such as granisetron, may be associated with arrhythmias or ECG abnormalities. Three ECGs were performed on 588 patients in a randomized, parallel group, double-blind, double-dummy study: at baseline before treatment, the first day of chemotherapy, and 5 to 7 days after starting chemotherapy. QTcF prolongation greater than 450 milliseconds was seen in a total of 11 (1.9%) patients after receiving granisetron, 8 (2.7%) on oral granisetron, and 3 (1.1%) on the patch. No new QTcF prolongation greater than 480 milliseconds was observed in any patient in this study. No arrhythmias were detected in this study.

Adverse reactions reported in clinical trials with other formulations of granisetron include the following:

*Gastrointestinal:* abdominal pain, diarrhea, constipation, elevation of ALT and AST levels, nausea and vomiting

*Cardiovascular:* hypertension, hypotension, angina pectoris, atrial fibrillation and syncope have been observed rarely

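### Bowel events count as adverse events, but the Section 7.2 procedures do not elicit them while the patch is worn at home, despite the masking warning in Section 12.2.1

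*Combined protocol and SAP*

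**What the plan says.** **The risk.** Section 12.2.1 warns: "The use of granisetron in patients may mask a progressive ileus and/or gastric distention caused by the underlying condition". From the chemotherapy trials, Section 12.3.1 reports: "The most common adverse reaction was constipation that occurred in 5.4% of patients in the Sancuso group", against 3.0% on oral granisetron. Overall, "Adverse reactions occurred in 8.7% (35/404) of patients receiving Sancuso". At entry, Section 3.2 excludes patients with: "History or diagnosis of gastrointestinal obstruction or ileus".

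**The home procedures.** Section 7.2.1 describes one daily record: "the patient will be asked to record their instances of nausea and vomiting on a daily basis for up to five days after surgery". A telephone call at 120 hours picks up those entries, and the text adds: "The case manager will also check the status of the patch and any medications that were taken as a result of nausea and vomiting". Seven days after the patch comes off, "a case manager will call the patient a final time to collect adverse events and to assess patient satisfaction with the patch". Section 7.2.4 describes the last contact differently: "The patient will be contacted by phone to record any possible side-effects they may have experienced since the removal of the patch". The opening text of 7.2 also ties the final interview to effects after the drug is stopped.

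**The general safety provisions.** Section 7.2.3 has treatment-emergent events of any cause recorded until day 5 after surgery. Section 11.4 starts adverse event assessment at patch placement and includes the 120-hour interview. Section 21.2 sends every adverse event, labelled ones included, to the case report form. Section 11.3 gives no method of its own and refers back to 7.2.

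**The concern.** The protocol names a bowel risk that the drug may conceal, and a commonest reaction that is also a bowel event. Yet no section contains a question about bowel movement, gas, distention or abdominal pain. The only daily home record described follows the symptoms the drug is meant to suppress.

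The population makes this relevant. Section 3.1 admits procedures under general anesthesia expected to last more than 1 and up to 5 hours, Section 3.2 rules out only eye surgery by type, and Section 7.2.3 includes intraoperative IV opioids. Abdominal surgery is therefore eligible. The exclusion for ileus or obstruction works at entry and cannot detect an ileus that develops afterwards.

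Two things are at stake. One is ascertainment: side-effect incidence is the second aim in Section 1.1 and a secondary endpoint in Section 1.3, and Sections 11.8 and 21.8 rest stopping decisions partly on a change in event frequency. The other is timeliness: a patient with few symptoms and a developing ileus may not be noticed until a late contact.

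**Working it through.** No design figure depends on this point, so the main check is to follow the contacts in order.

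| Contact | Content listed | Adverse event question? |
|---|---|---|
| Day of surgery, before anesthesia (7.2.3) | Patch check; local and systemic side effects | Yes |
| PACU discharge (7.2.3) | Nausea, vomiting, rescue | Not listed |
| Daily diary at home, to day 5 (7.2.1) | Nausea and vomiting | Not listed |
| 120-hour call or bedside visit (7.2.1, 7.2.3) | Diary entries, patch status, medication for nausea and vomiting | Not listed in 7.2; implied by 7.2.3 and 11.4 |
| Final call, 7 days after removal | 7.2.1: adverse events, no time limit. 7.2 and 7.2.4: effects after removal | Yes, but the window is described in two ways |

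**Consequence of the two wordings.** No scheduled contact is described between discharge and 120 hours for a patient at home. For same-day discharge that is up to 120/24 = 5 days.
- If the final call covers only the time since removal, no listed question reaches those days.
- If it covers all adverse events, they are reached by unprompted recall at 5 + 7 = 12 days after surgery. With the patch applied 1 to 2 days before surgery, this is 13 to 14 days after placement.

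**Checking the quoted rates.** 35/404 = 8.7% and 29/406 = 7.1%, as stated. The 5.4% agrees with 22/404; the count of 22 is inferred, as the protocol gives only the percentage.

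**Expected constipation cases among the 60 evaluable patients (Section 16.0).**
- At 5.4%: 60 × 0.054 = 3.24 cases; chance of at least one, 1 − 0.946^60 = 0.964.
- At 3.0%: 60 × 0.030 = 1.8 cases; chance of at least one, 1 − 0.970^60 = 0.839.

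**Sensitivity to under-recording.** One missed case moves the recorded rate by 1/60 = 1.7 percentage points. The documents give no capture proportion c, so it is assumed here:
- c = 0.75: 0.75 × 5.4% = 4.05%
- c = 0.50: 0.50 × 5.4% = 2.7%, below the 3.0% quoted for oral granisetron
- c = 0.25: 0.25 × 5.4% = 1.35%

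**Ileus.** The documents give no rate. For assumed rates of 0.5%, 1%, 2% and 5%, the chance of at least one case in 60, 1 − (1 − p)^60, is 26%, 45%, 70% and 95%. This range says whether a case would arise, not whether it would be masked or found late.

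**The case against.** The strongest reply is that adverse event capture is already in the protocol. Events of any cause are recorded to day 5, assessment starts at patch placement, the case report form takes labelled events (constipation is one), and 7.2.1 itself provides a final adverse event call. This stands, and it defeats the reading that bowel harm lies outside the safety plan. It does not supply a method. Section 21.2 governs what is recorded once an event is observed or reported, and Section 11.3 returns the reader to 7.2, where the 120-hour question is absent.

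A second reply is that 7.2.3 says the diary holds whatever the follow-up calls will ask for, so it may be wider than 7.2.1 suggests. The diary form, call script and adverse event forms are not among the documents, so this remains open. If those forms already carry bowel items, only the protocol text needs aligning.

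Third, other safeguards exist. Inpatients are seen at the bedside, prolonged hospitalization is a serious adverse event, and Section 3.3.2 provides a telephone number for problems, although under a heading about withdrawn subjects. These also stand. They depend on the patient being in hospital, becoming seriously ill, or choosing to call.

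A reader might also infer that the plan relies on nausea and vomiting to detect bowel trouble, in contradiction of its own warning. No section says so: these symptoms are collected as the efficacy outcome.

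**Conclusion.** The point holds as a gap in how safety data are elicited. General provisions cover bowel events, but the operating procedures contain no listed question that draws them out during wear at home, and the final call has two incompatible descriptions. Constipation may be under-recorded, and a masked ileus may come to notice late. The change is worth making; it does not affect the sample size or the primary analysis.

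The size of the loss cannot be computed. The 3.2 expected cases rest on a chemotherapy rate that may not carry over to surgical patients given opioids, and the capture proportions above are assumptions. The documents also give no share of abdominal surgery or of same-day discharge.

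Three stronger readings are not supported:
- The 96% chance of at least one constipation case shows that constipation is likely to occur. It does not measure how many cases would be missed.
- Sections 3.3.1 and 12.2.1 do not conflict. One lists removal criteria and the other gives a warning.
- A patient with masked ileus and no nausea, vomiting or antiemetic use is not misclassified as a complete responder, because that patient meets the definition in Section 1.2. The issue is safety ascertainment.

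**What to change.** 1. Reconcile Sections 7.2, 7.2.1, 7.2.3, 7.2.4, 11.3 and 11.4. State that the 120-hour contact includes an adverse event question and that the final call covers the whole period since patch placement. Align the day-5 end of event recording in 7.2.3 with the later call.
2. Add three daily yes/no items to the paper diary: bowel movement, passage of gas, and abdominal distention. Ask the same scripted questions at the two planned calls, or at the bedside for inpatients.
3. Record constipation and ileus as solicited events, marked separately from spontaneous reports. Pass any answer of concern to the investigator for review. No clinical management rule is proposed.

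The cost is three diary lines, a short script for contacts already planned, and a case report form field. The downside is that solicited reporting will raise the recorded constipation rate and make it less comparable with the 5.4% from the chemotherapy trials. Reporting solicited and spontaneous events separately keeps that difference visible.

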### **12.2.2 Skin Reactions**

In clinical trials with Sancuso, application site reactions were reported that were generally mild in intensity and did not lead to discontinuation of use. The incidence of reactions was comparable with placebo.

If severe reactions, or a generalized skin reaction occur (e.g., allergic rash, including erythematous, macular, papular rash or pruritus), the patch must be removed.

### **12.2.3 Exposure to Sunlight**

Granisetron may be affected by direct natural or artificial sunlight. Patients must be advised to cover the patch application site, e.g. with clothing, if there is a risk of exposure to sunlight throughout the period of wear and for 10 days following its removal because of a potential skin reaction [*see Nonclinical Toxicology (13.3)*].

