### **3.3.2 Follow-up for withdrawn subjects**

Patients will be routinely followed-up for additional 7 days after the patch removal. They will be contacted by phone (if discharged) or visited on the floor (if in the hospital). If discharged, they will be provided with the phone number of the PI and research staff in case of occurrence of any problems.

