### **7.2 Study Procedures**

Patients will be recruited from the surgical population undergoing preoperative evaluation in Anesthesiology Preoperative Evaluation Clinic at Hershey Med. Ctr. (~15,000 per year). Selected patients (ASA 1-3, N=60) with history of severe PONV after one or more of previous general anesthesia, and scheduled to undergo surgical procedures with general anesthesia will be enrolled into IRB approved protocol. The patch will be placed by the patient at home 24 – 48 hours before surgery as directed by the doctor. The subsequent standardized general anesthesia protocol for elective surgery will include general endotracheal anesthesia with sevofluran, including standard intraoperative PONV prophylaxis (IV dexamethasone and 4 mg and diphenhydramine 25 mg ). Postoperative evaluation will include recording of incidence and severity of PONV at the time of discharge from PACU (acute PONV), and at 120 hrs (delayed or post discharge PONV). The final phone interview will be performed 7 days after patch removal in order to capture possible side effects after discontinuation of medication.

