### **7.3 Duration of Participation**

Patient will remain in the study until the final follow-up phone call has been made (7 days

following removal of the patch).

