##### **7.4.2 Treatment Regimen**

Study Subjects will receive one patch and it will be applied to the upper arm. The patch will stay in place for 120 hours postoperatively.

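### The last scheduled safety contact falls 3 days before the end of the 10-day skin precaution, and Section 7.2.3 ends adverse event recording at patch removal

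*Combined protocol and SAP*

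**What the plan says.** **Precaution.** Section 12.2.3 (Exposure to Sunlight) asks that patients be told to keep the application site covered where sun exposure is a risk, "throughout the period of wear and for 10 days following its removal because of a potential skin reaction".

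**Removal.** Section 7.4.2: "The patch will stay in place for 120 hours postoperatively".

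**Last contact.** The protocol gives the same interval throughout:
- Section 7.2: "The final phone interview will be performed 7 days after patch removal in order to capture possible side effects after discontinuation of medication".
- Section 7.2.1: "One week after removal of patch (120h post-op + 7 days), a case manager will call the patient a final time". This call collects adverse events and patient satisfaction.
- Section 11.4: "A second and final phone interview will be performed 7 days after patch removal".
- Section 3.3.2, under the heading for withdrawn subjects: "Patients will be routinely followed-up for additional 7 days after the patch removal".
- Section 7.3 ends participation at that call.

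Section 7.2.4 describes a post-removal side-effect call but gives it no date. No later contact is scheduled anywhere.

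**Recording period.** Section 7.2.3 says that treatment-emergent adverse events, whatever their suspected cause, are recorded up to 5 days after surgery.

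**Use of the data.** Incidence and seriousness of side effects is the second specific aim (Section 1.1). Frequency and type of side effects is a secondary endpoint (Section 1.3).

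**The concern.** The final call exists to pick up effects that appear after the patch comes off. The only post-removal period that the protocol itself links to a possible drug-related reaction is the 10 days in Section 12.2.3. The call closes data collection before that period ends, and no reason is given for choosing 7 days.

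At stake is the completeness of a secondary safety outcome. A reaction that begins after the last call can be missed but cannot be over-counted, so any error runs toward too few events. The study has a single arm, and its historical comparison in Section 9.1 concerns failure of prophylaxis only. The side-effect counts will therefore be read as they stand, with no concurrent group subject to the same shortfall.

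The recording period in Section 7.2.3 raises a separate problem of consistency. Read literally, it ends when the patch is removed, so anything reported at the final call falls outside it.

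**Working it through.** This is timeline arithmetic. Alpha, power and sample size play no part.

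**Inputs**
- Patch applied 24 to 48 hours before surgery (7.2, 7.2.2).
- Patch removed at 120 hours after surgery (7.4.2).
- Final call 7 days after removal (3.3.2, 7.2, 7.2.1, 7.3, 11.4).
- Precaution lasts through wear and for 10 days after removal (12.2.3).
- Treatment-emergent adverse events recorded until 5 days after surgery (7.2.3).

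**Step 1. The plan's own date for the last contact.** Removal is at 120/24 = postoperative day 5. The last contact is 5 + 7 = day 12, which agrees with the definition in 7.2.1.

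**Step 2. End of the precaution.** 5 + 10 = day 15.

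**Step 3. Gap.** 15 − 12 = 3 days, the same as 10 − 7. As a share of the post-removal period, 3/10 = 30%.

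**Step 4. Share of the whole precaution, including wear.**

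| Application before surgery | Days of wear | Wear + 10 days | Share after last contact |
|---|---|---|---|
| 24 h | (24 + 120)/24 = 6 | 16 | 3/16 = 18.8% |
| 48 h | (48 + 120)/24 = 7 | 17 | 3/17 = 17.6% |

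**Step 5. If 7.2.3 governs recording.** Recording stops on day 5 and removal is on day 5, so 5 − 5 = 0 post-removal days are covered. The shortfall against the precaution is 10 − 0 = 10 days, and against the planned call it is 7 days.

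**Step 6. What else could capture a late reaction.**
- Section 3.3.2 gives discharged patients a telephone number for problems. This is patient-initiated, and it appears under the heading for withdrawn subjects.
- Section 21.2 follows events believed to be associated with the drug until they resolve or stabilize. This covers a reaction already known by the day-7 call. It does not detect one that starts afterwards.

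What remains without scheduled capture is a new reaction with onset on post-removal days 8 to 10.

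**The case against.** The strongest reply is that the 10 days is not a monitoring period. Section 12.2.3 is conditional advice about avoiding a trigger. It cross-refers to a nonclinical toxicology Section 13.3 that this protocol does not contain (its Section 13 is on potential benefits), so it looks like imported product text whose basis cannot be seen here. How long to avoid sunlight and how long to collect adverse events are different questions, and nowhere does the protocol promise 10 days of collection. This stands: Sections 12.2.3 and 7.2 do not contradict each other. What survives is narrower. The advice gives a possible skin reaction as its reason, and the call's stated purpose is to capture effects after discontinuation, so it is fair to ask why the call comes first.

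A reader might also infer three stronger things, none of which the documents support:

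- **That days 8 to 10 are never assessed.** Patients can telephone, and events already reported are followed up. Only scheduled capture is missing.
- **That the side-effect rate will be under-counted, by 30% or some other known amount.** The 30% is a share of calendar days. No rate of late reactions is given, and the precaution matters only to patients with sun exposure.
- **That the missed events are among the likeliest with a patch.** This would borrow from general application-site reactions, which Section 12.2.2 describes as generally mild and similar in incidence to placebo. The reaction in Section 12.2.3 is tied to sunlight. Table 1 in Section 12.3.1 (events of at least 3% in either group) lists only constipation and headache, and Section 12.3.2 says that frequency often cannot be estimated reliably from postmarketing reports.

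**Conclusion.** The point holds as a minor gap in safety follow-up together with one real inconsistency.

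- **Gap.** No scheduled contact covers new skin reactions on post-removal days 8 to 10. Late site reactions could be under-ascertained, by an amount that the documents do not allow to be estimated.
- **Inconsistency.** The recording period in Section 7.2.3 ends at scheduled removal, while Sections 7.2, 7.2.1 and 11.4 plan a side-effect call a week later. These must be reconciled whatever is decided about the 10 days.

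The primary endpoint is measured over 120 hours and is unaffected.

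The 3-day figure assumes removal at 120 hours and a call exactly 7 days later. The importance of the gap rests on reading the sunlight advice as a sign of when a reaction might occur. That is a reasonable inference, but the protocol does not say so. The change is a cheap improvement and not a condition for the trial's validity.

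**What to change.** 1. Move the single final call to at least 10 days after patch removal in Sections 3.3.2, 7.2, 7.2.1, 7.3 and 11.4, and give the same date in 7.2.4, which now has none.
2. Add a specific question about application-site reactions to the call script, including the date of onset.
3. In Section 7.2.3, extend the recording of treatment-emergent adverse events so that it runs to that call. Without this, the other edits leave the stated recording period ending at removal.
4. If the sponsor prefers to keep 7 days, say why in Section 11.4, and still make 7.2.3 agree with the call.

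**Cost.** The number of calls and the treatment are unchanged. Participation lengthens by 3 days (last contact on postoperative day 15, not day 12), and patients recall side effects over a slightly longer period. The satisfaction rating, a secondary endpoint collected at the same call, would come 3 days later for every patient. Collecting satisfaction at the 120-hour call avoids that delay.
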